9.2.4 Frequency of Assessments

An overview of the planned assessments is provided in [Table 4](#) and [Table 5](#).

Company substance code INN
MS202559_0001

COPD cohort

The participants will visit the sites as per routine practice and the timing of the visits and assessments performed will be as per the treating physician judgment. Results of the assessments will be collected upon availability.

Table 4 Planned Assessments: COPD Cohort

Assessments	Baseline Visit Day 0	Exacerbation Visits (moderate and severe)	End of Study 3 Months ± 14 days	Comments
Participant Informed consent	X			
Inclusion/Exclusion criteria	X			
Demographics	X			
Medical history	X			
Physical examination	X	X	X	
COPD history	X			
Baseline Medication	X			
Record changes in medication (COPD and other)		X	X	Changes in medication means changes of medication at the time of the current visit (including newly prescribed medication) as compared to the baseline visit (Day 0)
Comorbidities	X			
Smoking status	X			
Exacerbation history	X			
Moderate and severe exacerbations during observation period		X	X	Moderate and severe exacerbations should be recorded that occurred between Day 0 and the current visit (including exacerbations at the time of the visit)
Lung function (Plethysmography)	X	X	X	For the Baseline visit (Day 0), data from the past 2 weeks are acceptable.
End of study satisfaction questionnaire			X	
(S)AE recording	→			Continuous recording
Serious Adverse Device Effects (SADE) and Device Deficiency (DD) reporting	→			Continuous reporting
CAT collection via App	Daily at home			
Data collection via App (labeling events and activities)	Daily at home			Includes medication data used to identify mild exacerbations

Laboratory values (if available from clinical practice)				For the Baseline visit (Day 0), data from the past 2 weeks are acceptable.
C-reactive protein (CRP)	X	X	X	
Procalcitonin	X	X	X	
Blood count (including eosinophiles, neutrophiles, Hb)	X	X	X	
Capillary blood gas analysis: pO ₂ and pCO ₂ ; SpO ₂	X	X	X	

Table 5 Planned Assessments Calibration Cohort

Assessments	Day 0	End of Study 2 Weeks	Comments
Participant informed consent	X		
Inclusion/Exclusion criteria	X		Assessed by Investigator by review of medical history and/or participant reported medical history
Demographics	X		
Medical history	X		
Comorbidities	X		
Medication	X	X	
End of Study satisfaction questionnaire		X	
(S)AE recording	→		Continuous recording
SADE and DD reporting	→		Continuous reporting

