### 2.1.3 Lung function and laboratory values

The following variables will be measured at baseline, at each exacerbation visit, and at end of study visit.

- Current or last available body plethysmography parameters:
  - FEV1 [L],
  - FVC [L] (forced vital capacity),
  - FEV1/FVC [],
  - TLC [L] (total lung capacity),
  - RV [L] (residual volume),
  - FRCpleth [L] (functional residual capacity),
  - IC [L] (inspiratory capacity),

- Raw [kPa s L-1] (=ratio of sRaw to FRCpleth; airway resistance),
- sRaw [kPa s] (specific airway resistance),
- TV [L] (mean tidal volume),
- ERV [L] (expiratory reserve volume),
- IRV [L] (inspiratory reserve volume)
- Blood gas analysis:
  - (capillary) pO2 [mmHg]
  - O2 saturation [%]
  - pCO2 [mmHg]
- Serum CRP [mg/l] and serum procalcitonin levels [ng/ml]
- Blood count (CBC with differential):
  - Hb [g/dL]
  - Hct [%]
  - Erythrocyte count [ $10^6/\mu\text{L}$ ]
  - MCV [fL]
  - MCH [pg]
  - MCHC [g/dL]
  - Reticulocytes [ $\times 10^3/\mu\text{L}$ ] [% (of erythrocytes)]
  - RDW []
  - platelet count [ $10^3/\mu\text{L}$ ]
  - WBC count [ $\times 10^3/\mu\text{L}$ ]
  - Lymphocytes [ $\times 10^3/\mu\text{L}$ ] [%]
  - Monocytes [ $\times 10^3/\mu\text{L}$ ] [%]
  - Neutrophils [ $\times 10^3/\mu\text{L}$ ] [%]
  - Eosinophils [ $\times 10^3/\mu\text{L}$ ] [%]
  - Basophils [ $\times 10^3/\mu\text{L}$ ] [%]

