### 3.4.4 Handling of missing data

For variables obtained only at the baseline visit, missing values will not be replaced.

For the self-reported satisfaction questionnaire items, collected at the end of study visit, missing values will not be replaced. For variables measured daily during the observation period such as sensor-generated data, CAT score, and labelling information, missing data will not be imputed for all descriptive statistical analyses performed. The CAT score and derived sensor variables may be imputed for the purpose of building machine learning models if needed to avoid loss of instances using a suitable imputation method (e.g., LOCF, Forward filling, multiple imputation [MI], recursive imputation, median imputation). Sensitivity analyses will be conducted to assess the impact of imputation.

For variables with values collected at baseline, at the exacerbation visit and at end of study visit, missing values will not be imputed for all descriptive statistical analyses. Lung function parameters and lab values may be imputed for the purpose of building machine learning models if needed to avoid loss of instances by LOCF method if the last (previous) available value is recorded within 2 weeks before the date of the visit of interest. In cases where no value for a variable is available for a participant, imputation strategies across instances may be used (e.g., median imputation or iterative imputation methods). Sensitivity analyses will be conducted to assess the impact of imputation.

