	Lung function parameters by plethysmography (see section 2.1.3, 13 parameters)	Baseline (Day 0), End of study visit
	Laboratory values (see section 2.1.3, 20 parameters): Current or last available (capillary) pO 2 , O 2 saturation and pCO 2 ; Serum CRP and serum procalcitonin levels; blood count (CBC with differential)	Baseline (Day 0), End of study visit
	Exacerbation count by mild, moderate or severe exacerbation.	End of study visit

For each pair of groups (x, y) and for each assessment time point, a table with x and y parameter groups indexing rows and columns respectively, will be provided to display coefficient of correlation and 95% CI for all parameter pairs. To provide a visualization, the tables will be plotted as matrix heatmaps displaying the correlation coefficient point estimates.

#### 3.4.5.4 Secondary Objective 4

Sensor derived data may be related to the CAT score, therefore, an additional objective is to investigate whether changes in physical activity, heart rate, heart rate variability, temperature, respiration rate, cough frequency, and sleep pattern in the 3-month observation period, are associated with changes of the patient self-assessed symptoms (CAT).

This analysis will be performed on the COPD participants set.

The following analyses will be conducted in this order:

- Linear mixed model with the patient self-assessed symptoms, CAT score, mean value assessed on a 7-day basis as the response variable and the mean values of physical activity, heart rate,

heart rate variability, temperature, respiration rate, cough frequency also assessed in the same timeframe as the independent variables. Individual trajectories will be investigated. A model including the change of each sensor variable, the time (7-day period) as fixed effect will be tested. Interaction terms between the time and each sensor variable will be included in the model and potentially patient-level random intercepts and slopes will also be included in the model. Other covariates such as age, sex, smoking status, medical history will be considered. The same model will be considered with the absolute change of the CAT score and the absolute change of the sensor variables.

$$Y_{ij} = (\alpha + a_i) + (\beta + b_i) X_{ij} + \xi_{ij}$$

where  $a_i$  is the random intercept,  $b_i$  is the random slope for the  $j^{\text{th}}$  observation of the individual  $i$

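### The SAP's last-available rule for lung function and blood gases in objective 3 has no age limit, so End of Study sensor data can be paired with Day 0 or exacerbation-visit values

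*SAP*

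**What the plan says.** SAP 3.4.5.3 pairs each sensor variable with lung function and laboratory values at Day 0 and End of Study. The laboratory row reads "Laboratory values (see section 2.1.3, 20 parameters): Current or last available (capillary" and continues with the blood gases, then, after semicolons, CRP with procalcitonin, and the blood count. The lung-function row, "Lung function parameters by plethysmography (see section 2.1.3, 13 parameters", takes its definition from SAP 2.1.3, where the list opens with "Current or last available body plethysmography parameters". No maximum age is given in either section. SAP 2.1.3 also says: "The following variables will be measured at baseline, at each exacerbation visit, and at end of study visit".

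Four other provisions bear on this:

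- Protocol 9.1.2.2, Table 1 defines outcome 3b as values assessed at baseline (Day 0) and at study end.
- Protocol 9.2.4, Table 4 says, for both lung function and laboratory values: "For the Baseline visit (Day 0), data from the past 2 weeks are acceptable". It gives no window for End of Study. It collects laboratory values only if clinical practice supplies them.
- SAP 3.4.4 says of variables collected at these visits that "missing values will not be imputed for all descriptive statistical analyses". For machine-learning models it allows filling "by LOCF method if the last (previous) available value is recorded within 2 weeks before the date of the visit of interest". Protocol 9.7.1.2 has the same rule.
- SAP 1.3.1 excludes anyone with a moderate or severe exacerbation in the 6 weeks before inclusion.

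**The concern.** A last-available rule without an age limit is carry-forward without a limit. Followed as written, it drops the protocol's Day 0 window. At End of Study it lets a value from an earlier visit stand in for one that the protocol defines as a study-end value. The correlations would then have a looser rule than the machine-learning models, the only analyses for which carry-forward is expressly allowed.

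Missing End of Study values are likely: laboratory tests depend on routine practice, and Protocol 9.1.1 allows End of Study contact by telephone. Exacerbation visits are scheduled plethysmography and laboratory time points, so the last value on file may have been taken during an exacerbation. Sensor data from a stable participant at study end would then be paired with lung function or blood gases from another time and another clinical state. Estimating these correlations is the purpose of objective 3.

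**Working it through.** **Inputs.** Event rate: 2 moderate or severe exacerbations per year, Poisson (Protocol 9.5, SAP 1.3.2). End of Study: 3 months ± 14 days, taken as Day 77, 91 or 105. Evaluable participants: 60. Exacerbation-free interval before Day 0: 42 days. The proportion of missing End of Study values is not given; I use 10% to 50% as an assumption, independent of exacerbations.

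**The plan's own figure.** P(at least one event) = 1 − exp(−0.5) = 39.3%. This agrees with the roughly 40% in Protocol 9.9.

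**Day 0.** The protocol window is 14 days and the exacerbation-free interval is 42 days. Since 14 < 42, a value inside the window cannot come from a moderate or severe exacerbation. Such a value could enter at Day 0 only if the SAP wording overrode Table 4.

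**End of Study.** Daily rate = 2/365.25 = 0.005476.

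- P(no event by day T) = exp(−0.005476 × T).
- P(latest onset more than 14 days before T) = exp(−0.005476 × 14) − exp(−0.005476 × T), where the first term is 0.926.

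| End of Study day | No in-study event | Latest onset more than 14 days earlier | Of 60 |
|---|---|---|---|
| 77 | 65.6% | 0.926 − 0.656 = 27.0% | 16 |
| 91 | 60.8% | 0.926 − 0.608 = 31.9% | 19 |
| 105 | 56.3% | 0.926 − 0.563 = 36.3% | 22 |

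A further 1 − 0.926 = 7.4% have an onset in the last 14 days, so a 14-day limit alone would not remove every value from an earlier exacerbation visit.

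These shares are ceilings, because the rule acts only where the current value is missing. At Day 91 with 10% to 50% missing:

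- Exacerbation value more than 14 days old: 19.1 × 0.10 to 19.1 × 0.50, about 2 to 10 of 60.
- Day 0 value carried: 36.5 × 0.10 to 36.5 × 0.50, about 4 to 18 of 60. It would be about 77 to 105 days old, or up to 105 + 14 = 119 days with the baseline look-back.

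**Effect on a correlation (illustration; every input is assumed).** Let the true correlation be r = 0.40, the missing fraction m, the correlation between a participant's carried and current value ρ = 0.5 to 0.7, and the shift of an exacerbation value δ = 1.5 to 2 SD in either direction. Let sensor data at End of Study be unrelated to having had an event, and let q = 0.392 × m. Then

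expected r = 0.40 × [1 − m(1 − ρ)] / √[1 + δ²q(1 − q)].

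- m = 10%: 0.35 to 0.37.
- m = 30%: 0.29 to 0.33. For example, with ρ = 0.7 and δ = 1.5, q = 0.118 and 0.40 × 0.91 / √1.234 = 0.33.
- m = 50%: 0.23 to 0.29.

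**The case against.** The strongest reply is that this is a small wording gap in a secondary correlation analysis of a study that calls itself exploratory, and that the documents largely close it. Much of that stands, and it rules out several stronger readings that a reader might infer.

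- *Old exacerbation values at Day 0.* The documents do not support this if Table 4 governs collection: the 14-day window and the 6-week exclusion together rule it out. Only the SAP's failure to repeat the window leaves it open.
- *All laboratory values, including CRP.* In the laboratory row the wording most naturally attaches to the blood gases; CRP, procalcitonin and blood count follow after semicolons. In SAP 2.1.3 it precedes only plethysmography. The wider reading is possible but is not the natural one.
- *Direct breach of the no-imputation rule.* That rule names descriptive analyses, and neither document says whether correlations with confidence intervals are descriptive. The 2-week carry-forward limit is written for machine learning, and Table 4's window is for Day 0 only. No End of Study window is contradicted, because none is stated.
- *Only participants with an event are affected.* The larger group is those without one, who would carry a Day 0 value.

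The attenuation figures rest on assumptions. If participants with a past event also had lastingly different sensor data at study end, the bias could be smaller or run the other way. A date limit also costs precision.

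The reply does not remove the rule itself. At End of Study the SAP allows a value of any age for plethysmography and blood gases, where the outcome is defined as the value at study end.

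**Conclusion.** The point holds in limited form. For plethysmography and blood gases, and for all laboratory values on a wider reading, the SAP permits values of any age in the objective 3 correlations. This omits the protocol's Day 0 window and leaves End of Study open to unlimited carry-forward.

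The exposure is mainly at End of Study. About 61% of participants (56% to 66%) could carry a Day 0 value, and up to about 32% (27% to 36%) an exacerbation-visit value more than 14 days old, in each case only where the current value is missing. These shares rest on the plan's own rate of 2 events per year. The likely direction is weaker correlations; the amount cannot be fixed from the documents because they give no missing rate. No primary analysis and no sample-size figure is affected. The change is worth making because the rule as written gives a worse answer than a dated one and is cheap to correct.

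**What to change.** In SAP 2.1.3 and 3.4.5.3, replace the last-available wording with: *measured at the visit or within the 14 days before it; values from an earlier, separate exacerbation visit are not used; values measured at the End of Study visit itself are kept even if an exacerbation is present; otherwise missing.* Apply it at Day 0 and End of Study, and say which laboratory variables it covers. State in SAP 3.4.4 whether the objective 3 correlations count as descriptive. Report n for each correlation. The last-available version can be shown as a sensitivity analysis if wanted.

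The End of Study window and the exclusion of earlier exacerbation visits are additions; neither is already in Table 4 or SAP 3.4.4.

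The work is SAP wording and a date filter. The statistical cost is fewer pairs. With Fisher's transform, the 95% interval is tanh[atanh(r) ± 1.96/√(n − 3)]. For r = 0.40 it is 0.16 to 0.59 at n = 60, 0.11 to 0.63 at n = 42 (30% missing), and 0.05 to 0.66 at n = 30 (50% missing). That loss is noticeable if many End of Study tests are missing, which is why n should be shown.

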8.2 Secondary Objectives

3. To evaluate the correlation of sensor collected data with
 - a) patients' self-assessed health status and symptoms (CAT) at baseline and study end,
 - b) lung function and lab values at baseline and study end,
 - c) and with history of mild, moderate and severe exacerbations at study end.
4. Sensor derived data may be related to the CAT score, therefore, an additional objective is to investigate whether changes in physical activity, heart rate, heart rate variability, temperature, respiration rate, cough frequency, and sleep pattern in the 3-month observation period, are associated with changes of the patient self-assessed symptoms (CAT).
5. To predict the CAT score and changes thereof by building a statistical model employing sensor-derived data and demographic and medical covariates.

CCI

A large black rectangular box covers the majority of the page below the 'CCI' text, indicating that the content has been redacted.

9 Research Methods

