- The analysis above will be repeated on the COPD participants with severe/moderate exacerbations in the time-window considering the 14 days prior the exacerbations. Daily values of the CAT score and of the physical activity, heart rate, heart rate variability, temperature, respiration rate, cough frequency, and sleep pattern will be considered in the model.

The relation between the change of the patient self-assessed symptoms (CAT score) and the changes of the physical activity, heart rate, heart rate variability, temperature, respiration rate, cough frequency, and sleep pattern during the 3-month observation period will be further evaluated using linear spline regression to infer the location of the changepoints.

[figure not shown]
#### 3.4.5.5 Secondary Objective 5

To predict the CAT score and changes thereof by building a statistical model employing sensor-derived data and demographic and medical covariates

[figure not shown]
This analysis will be performed on the COPD participants set.

Similar to Primary Objective 2, different machine learning algorithms will be evaluated, and their performance will be assessed by estimating their accuracy, specificity, sensitivity, and area under ROC metrics. Other usual evaluation metrics such as precision, positive predictive value (PPV), negative predictive value (NPV), F1-score will be computed.

[figure not shown]
CCI

CCI

CCI

CCI

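### The 7-day mixed model for objective 4 lists six sensor domains and leaves out sleep pattern, which the objective and its other two analyses include

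*SAP*

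**What the plan says.** Protocol 8.2 frames objective 4 around "changes in physical activity, heart rate, heart rate variability, temperature, respiration rate, cough frequency, and sleep pattern in the 3-month observation period" and their association with changes in CAT. SAP 1.1 and the opening of SAP 3.4.5.4 restate it with the same seven domains.

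SAP 3.4.5.4 then introduces its analyses with "The following analyses will be conducted in this order". The first is a linear mixed model on the COPD participants set. It takes the CAT score, "mean value assessed on a 7-day basis as the response variable and the mean values of physical activity, heart rate", and the sentence continues "heart rate variability, temperature, respiration rate, cough frequency also assessed in the same timeframe as the independent variables". The same bullet adds a change version: "A model including the change of each sensor variable, the time (7-day period) as fixed effect will be tested". It provides for interactions of time with each sensor variable, possible patient-level random intercepts and slopes, and patient covariates such as age and sex.

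The second analysis is presented as a repetition of the first, restricted to participants with a severe or moderate exacerbation and to the 14 days before it, using daily values. Its list closes with "heart rate variability, temperature, respiration rate, cough frequency, and sleep pattern will be considered in the model". A linear spline regression then relates change in CAT to change in all seven domains over the 3 months, with the aim of locating changepoints.

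**The concern.** Objective, first model, repeat and spline should cover the same domains unless the SAP explains a difference. One list is a term short, and it belongs to the first analysis in the sequence. That model is the only mixed model using the whole COPD set across the full observation period, with time interactions and possible patient-level random effects.

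A programmer who follows the sentence as written will fit six domains. The output will then have no weekly sleep coefficient and no sleep-by-time interaction for the full cohort. Adding sleep after the data are seen would be an unplanned change to a stated predictor list. Adding it now is a wording correction.

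**Working it through.** The check is mainly a comparison of lists.

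| Place | Domains named | Sleep pattern |
|---|---|---|
| Protocol 8.2, objective 4 | 7 | yes |
| SAP 1.1, objective 4 | 7 | yes |
| SAP 3.4.5.4, opening statement | 7 | yes |
| SAP 3.4.5.4, 7-day mixed model | 6 | **no** |
| SAP 3.4.5.4, 14-day pre-exacerbation model | 7 | yes |
| SAP 3.4.5.4, spline regression | 7 | yes |

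Count for the 7-day model: two domains at the start of the list (physical activity, heart rate) plus four in the remainder (heart rate variability, temperature, respiration rate, cough frequency) make 6. The difference from the objective is 7 − 6 = 1, and the missing item is sleep pattern.

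**Does other text supply the missing term?**

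- The extra covariates in the same bullet are patient characteristics. Sleep is not among the examples.
- SAP 3.4.2 says all available features will be considered, but in the predictive modelling. Its sentence on objective 4 adds only smoking status and other baseline covariates.
- The change version refers to each sensor variable without a new list. SAP 2.1.4 places sleep under sensor measurements, so the phrase can include sleep. The only list in that bullet has six domains, so it can also be read without it.
- The predictor sentence is complete, with no blacked-out text inside it.

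**Is sleep usable in this model?** SAP 2.1.4 defines it numerically, as hours of sleep, and SAP 3.4.5.1 and 3.4.5.3 use it in that form. A 7-day mean needs no new variable.

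**How many participants would the pre-exacerbation mixed model cover?** Inputs from Protocol 9.5 and SAP 1.3.2: 2 moderate or severe events per year, Poisson counts, 60 evaluable participants.

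- Expected events per participant in 3 months: 2 × 3/12 = 0.5.
- Probability of at least one: 1 − exp(−0.5) = 1 − 0.607 = 0.393, about 39%.
- Of 60 participants: 60 × 0.393 = 23.6, about 24.

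Protocol 9.9 itself expects such events in roughly 40% of participants, which agrees.

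**The case against.** The strongest reply is that sleep is not neglected. The spline regression relates change in sleep to change in CAT over the 3 months, and nothing limits it to participants with exacerbations. Objective 3 correlates sleep with CAT at baseline and study end, and the objective 5 models may use it. A reader might infer that, for objective 4, sleep is modelled in only about 39% of participants. The documents do not support that: the figure applies to the mixed model alone. It still stands that the spline's stated purpose is to locate changepoints, so it does not clearly replace a full-cohort mixed-model estimate.

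A reader might also infer that the change version omits sleep. Its wording is ambiguous, so this is not established.

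Nor does the omission explain why the weekly and daily models cannot be compared directly. They already differ by design in time unit, population and window, and adding sleep would not remove those differences.

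It would also be too strong to call the 7-day model the main analysis. The SAP gives an order, not a ranking.

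Finally, the omission looks like a drafting slip. An analysis described as a repeat includes sleep, which suggests that the authors meant it to be in the model being repeated. That makes the point minor, but the list as written still directs a six-domain model.

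**Conclusion.** The point holds as a minor internal inconsistency in SAP 3.4.5.4. The first model omits one of the seven domains in the objective, without a reason, while the repeat and the spline regression include it. Taken literally, the only mixed model on the full COPD set over 3 months yields no sleep estimate. For objective 4, sleep is then covered by a mixed model only in those with a moderate or severe exacerbation, and otherwise by the spline regression.

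The 39% rests on the plan's rate of 0.5 events per 3 months and on the same Poisson rate for everyone. At the same mean, variation in rates between participants would lower it. The inconsistency itself does not depend on that number.

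Objective 4 is secondary, and Protocol section 7 calls the study exploratory, so correcting this is desirable rather than critical.

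**What to change.** In the first analysis of SAP 3.4.5.4, add sleep pattern (hours of sleep, 7-day mean) to the independent variables. In the same bullet, state that each sensor variable in the change version, and in the time interactions, includes sleep. If sleep was left out on purpose, say so and give the reason.

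The change takes a few words and needs no new data or derivation. The statistical cost is one more predictor, correlated with the others, and its time interaction. If all ten heart rate variability measures counted in SAP 3.4.5.1 are entered, and the other five domains contribute one term each, the list already holds 10 + 5 = 15 sensor terms. Sleep would be the sixteenth. Sleep hours also rest on self-reported bedtimes (SAP 3.4.3), so the report should give the number of participant-weeks without a usable sleep value.
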